5.5 Concomitant Medications/Vaccinations (allowed & prohibited)

Medications or vaccinations specifically prohibited in the exclusion criteria are not allowed during the ongoing trial. If there is a clinical indication for one of these or other medications or vaccinations specifically prohibited during the trial, discontinuation from trial therapy or vaccination may be required. The investigator should discuss any questions regarding this with the Merck Clinical team. The final decision on any supportive therapy or vaccination rests with the investigator and/or the subject's primary physician.

5.5.1 Acceptable Concomitant Medications

All treatments that the investigator considers necessary for a subject's welfare may be administered at the discretion of the investigator in keeping with the community standards of medical care. All concomitant medication will be recorded on the case report form (CRF) including all prescription, over-the-counter (OTC), herbal supplements, and IV medications and fluids. If changes occur during

the trial period, documentation of drug dosage, frequency, route, and date may also be included on the CRF.

All concomitant medications received within 28 days before the first dose of trial treatment and 30 days after the last dose of trial treatment should be recorded. Concomitant medications administered after 30 days after the last dose of trial treatment should be recorded for SAEs and ECIs as defined in Section 7.2.

5.5.2 Prohibited Concomitant Medications

Subjects are prohibited from receiving the following therapies during the Screening and Treatment Phase (including retreatment for post-complete response relapse) of this trial:

- Antineoplastic systemic chemotherapy or biological therapy
- Immunotherapy not specified in this protocol
- Chemotherapy not specified in this protocol
- Investigational agents other than pembrolizumab
- Live vaccines within 30 days prior to the first dose of trial treatment and while participating in the trial. Examples of live vaccines include, but are not limited to, the following: measles, mumps, rubella, varicella/zoster, yellow fever, rabies, BCG, and typhoid vaccine.
- Systemic glucocorticoids for any purpose other than to modulate symptoms from an event of clinical interest of suspected immunologic etiology. The use of physiologic doses of corticosteroids may be approved after consultation with the Sponsor.

Subjects who, in the assessment by the investigator, require the use of any of the aforementioned treatments for clinical management should be removed from the trial. Subjects may receive other medications that the investigator deems to be medically necessary.

The Exclusion Criteria describes other medications which are prohibited in this trial.

There are no prohibited therapies during the Post-Treatment Follow-up Phase.

5.6 Rescue Medications & Supportive Care

5.6.1 Supportive Care Guidelines

Subjects should receive appropriate supportive care measures as deemed necessary by the treating investigator. Suggested supportive care measures for the management of adverse events with potential immunologic etiology are outlined below and in greater detail in the ECI guidance document. Where appropriate, these guidelines include the use of oral or intravenous treatment with corticosteroids as well as additional anti-inflammatory agents if symptoms do not improve with administration of corticosteroids. Note that several courses of steroid tapering may be necessary as

symptoms may worsen when the steroid dose is decreased. For each disorder, attempts should be made to rule out other causes such as metastatic disease or bacterial or viral infection, which might require additional supportive care. The treatment guidelines are intended to be applied when the investigator determines the events to be related to pembrolizumab.

Note: if after the evaluation the event is determined not to be related, the investigator is instructed to follow the ECI reporting guidance but does not need to follow the treatment guidance (as outlined in the ECI guidance document). Refer to Section 5.2.1 for dose modification.

It may be necessary to perform conditional procedures such as bronchoscopy, endoscopy, or skin photography as part of evaluation of the event. Suggested conditional procedures, as appropriate, can be found in the ECI guidance document.

- **Pneumonitis:**

- For **Grade 2 events**, treat with systemic corticosteroids. When symptoms improve to Grade 1 or less, steroid taper should be started and continued over no less than 4 weeks.
- For **Grade 3-4 events**, immediately treat with intravenous steroids. Administer additional anti-inflammatory measures, as needed.
- Add prophylactic antibiotics for opportunistic infections in the case of prolonged steroid administration.

- **Diarrhea/Colitis:**

Subjects should be carefully monitored for signs and symptoms of enterocolitis (such as diarrhea, abdominal pain, blood or mucus in stool, with or without fever) and of bowel perforation (such as peritoneal signs and ileus).

- All subjects who experience diarrhea/colitis should be advised to drink liberal quantities of clear fluids. If sufficient oral fluid intake is not feasible, fluid and electrolytes should be substituted via IV infusion. For Grade 2 or higher diarrhea, consider GI consultation and endoscopy to confirm or rule out colitis.
- For **Grade 2 diarrhea/colitis** that persists greater than 3 days, administer oral corticosteroids.
- For **Grade 3 or 4 diarrhea/colitis** that persists > 1 week, treat with intravenous steroids followed by high dose oral steroids.

- When symptoms improve to Grade 1 or less, steroid taper should be started and continued over no less than 4 weeks.
- **Type 1 diabetes mellitus (if new onset, including diabetic ketoacidosis [DKA]) or ≥ Grade 3 Hyperglycemia, if associated with ketosis (ketonuria) or metabolic acidosis (DKA)**
 - For **T1DM** or **Grade 3-4** Hyperglycemia
 - Insulin replacement therapy is recommended for Type I diabetes mellitus and for Grade 3-4 hyperglycemia associated with metabolic acidosis or ketonuria.
 - Evaluate patients with serum glucose and a metabolic panel, urine ketones, glycosylated hemoglobin, and C-peptide.
- **Hypophysitis:**
 - For **Grade 2** events, treat with corticosteroids. When symptoms improve to Grade 1 or less, steroid taper should be started and continued over no less than 4 weeks. Replacement of appropriate hormones may be required as the steroid dose is tapered.
 - For **Grade 3-4** events, treat with an initial dose of IV corticosteroids followed by oral corticosteroids. When symptoms improve to Grade 1 or less, steroid taper should be started and continued over no less than 4 weeks. Replacement of appropriate hormones may be required as the steroid dose is tapered.
- **Hyperthyroidism or Hypothyroidism:**

Thyroid disorders can occur at any time during treatment. Monitor patients for changes in thyroid function (at the start of treatment, periodically during treatment, and as indicated based on clinical evaluation) and for clinical signs and symptoms of thyroid disorders.

 - **Grade 2** hyperthyroidism events (and **Grade 2-4** hypothyroidism):
 - In hyperthyroidism, non-selective beta-blockers (e.g. propranolol) are suggested as initial therapy.

- In hypothyroidism, thyroid hormone replacement therapy, with levothyroxine or liothyronine, is indicated per standard of care.
 - **Grade 3-4** hyperthyroidism
 - Treat with an initial dose of IV corticosteroid followed by oral corticosteroids. When symptoms improve to Grade 1 or less, steroid taper should be started and continued over no less than 4 weeks. Replacement of appropriate hormones may be required as the steroid dose is tapered.
- **Hepatic:**
 - For **Grade 2** events, monitor liver function tests more frequently until returned to baseline values (consider weekly).
 - Treat with IV or oral corticosteroids
 - For **Grade 3-4** events, treat with intravenous corticosteroids for 24 to 48 hours.
 - When symptoms improve to Grade 1 or less, a steroid taper should be started and continued over no less than 4 weeks.
- **Renal Failure or Nephritis:**
 - For **Grade 2** events, treat with corticosteroids.
 - For **Grade 3-4** events, treat with systemic corticosteroids.
 - When symptoms improve to Grade 1 or less, steroid taper should be started and continued over no less than 4 weeks.
- **Management of Infusion Reactions:** Signs and symptoms usually develop during or shortly after drug infusion and generally resolve completely within 24 hours of completion of infusion.

Table 4 below shows treatment guidelines for subjects who experience an infusion reaction associated with administration of pembrolizumab (MK-3475).

NCI CTCAE Grade	Treatment	Premedication at subsequent dosing
Grade 1 Mild reaction; infusion interruption not indicated; intervention not indicated	Increase monitoring of vital signs as medically indicated until the subject is deemed medically stable in the opinion of the investigator.	None
Grade 2 Requires infusion interruption but responds promptly to symptomatic treatment (e.g., antihistamines, NSAIDS, narcotics, IV fluids); prophylactic medications indicated for < =24 hrs	
Stop Infusion and monitor symptoms.
 Additional appropriate medical therapy may include but is not limited to: 
 IV fluids Antihistamines NSAIDS Acetaminophen Narcotics 
Increase monitoring of vital signs as medically indicated until the subject is deemed medically stable in the opinion of the investigator.
 
If symptoms resolve within one hour of stopping drug infusion, the infusion may be restarted at 50% of the original infusion rate (e.g., from 100 mL/hr to 50 mL/hr). Otherwise dosing will be held until symptoms resolve and the subject should be premedicated for the next scheduled dose.
 
Subjects who develop Grade 2 toxicity despite adequate premedication should be permanently discontinued from further trial treatment administration.
	
Subject may be premedicated 1.5h (± 30 minutes) prior to infusion of pembrolizumab (MK-3475) with:
 
Diphenhydramine 50 mg po (or equivalent dose of antihistamine).
 
Acetaminophen 500-1000 mg po (or equivalent dose of antipyretic).

Grades 3 or 4 Grade 3: Prolonged (i.e., not rapidly responsive to symptomatic medication and/or brief interruption of infusion); recurrence of symptoms following initial improvement; hospitalization indicated for other clinical sequelae	
Stop Infusion.
 Additional appropriate medical therapy may include but is not limited to: 
 IV fluids Antihistamines NSAIDS Acetaminophen Narcotics Oxygen Pressors 	No subsequent dosing

NCI CTCAE Grade	Treatment	Premedication at subsequent dosing
(e.g., renal impairment, pulmonary infiltrates) Grade 4: Life-threatening; pressor or ventilatory support indicated	Corticosteroids Epinephrine Increase monitoring of vital signs as medically indicated until the subject is deemed medically stable in the opinion of the investigator. Hospitalization may be indicated. Subject is permanently discontinued from further trial treatment administration.	
Appropriate resuscitation equipment should be available in the room and a physician readily available during the period of drug administration.		

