5.2.1.2 Dose Modification

Adverse events (both non-serious and serious) associated with pembrolizumab exposure may represent an immunologic etiology. These adverse events may occur shortly after the first dose or several months after the last dose of treatment. Pembrolizumab must be withheld for drug-related toxicities and severe or life-threatening AEs as per Table 3 below. See Section 5.6.1 and Events of Clinical Interest Guidance Document for supportive care guidelines, including use of corticosteroids. There are no dose reductions for pembrolizumab. If the subject meets retreatment criteria, the full dose of 200 mg will be administered. If subjects do not meet retreatment criteria, then the dose of pembrolizumab will be SKIPPED.

Table 3
Dose Modification Guidelines for Drug-Related Adverse Events

Toxicity	Hold Treatment For Grade	Timing for Restarting Treatment	Discontinue Subject
Diarrhea/Colitis	2-3	Toxicity resolves to Grade 0-1.	Toxicity does not resolve within 12 weeks of last dose or inability to reduce corticosteroid to 10 mg or less of prednisone or equivalent per day within 12 weeks.
	4	Permanently discontinue	Permanently discontinue
AST, ALT, or Increased Bilirubin	2	Toxicity resolves to Grade 0-1	Toxicity does not resolve within 12 weeks of last dose.
	3-4	Permanently discontinue	Permanently discontinue
Type 1 diabetes mellitus (if new onset) or Hyperglycemia	T1DM or 3-4	Hold pembrolizumab for new onset Type 1 diabetes mellitus or Grade 3-4 hyperglycemia associated with evidence of beta cell failure.	Resume pembrolizumab when patients are clinically and metabolically stable.
Hypophysitis	2-3	Toxicity resolves to Grade 0-1	Toxicity does not resolve within 12 weeks of last dose or inability to reduce corticosteroid to 10 mg or less of prednisone or equivalent per day within 12 weeks.
	4	Permanently discontinue	Permanently discontinue
Hyperthyroidism	3	Toxicity resolves to Grade 0-1	Toxicity does not resolve within 12 weeks of last dose or inability to reduce corticosteroid to 10 mg

Toxicity	Hold Treatment For Grade	Timing for Restarting Treatment	Discontinue Subject
			or less of prednisone or equivalent per day within 12 weeks.
	4	Permanently discontinue	Permanently discontinue
Hypothyroidism	2-4	Therapy with pembrolizumab can be continued while treatment for the thyroid disorder is instituted	Therapy with pembrolizumab can be continued while treatment for the thyroid disorder is instituted.

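### Section 5.6.1 suggests steroids later for Grade 3-4 diarrhea/colitis (after more than 1 week) than for Grade 2 (after more than 3 days); the Grade 3-4 trigger should come no later than the Grade 2 one

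*Combined protocol and SAP*

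**What the plan says.** Section 5.6.1 (Supportive Care Guidelines) gives two consecutive steroid bullets for diarrhea/colitis. Grade 2 disease "that persists greater than 3 days, administer oral corticosteroids". Grade 3 or 4 disease "that persists > 1 week, treat with intravenous steroids followed by high dose oral steroids".

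The bullet just before them covers fluids and work-up at a wider range of grades: "For Grade 2 or higher diarrhea, consider GI consultation and endoscopy to confirm or rule out colitis". For every disorder in the section, "attempts should be made to rule out other causes such as metastatic disease or bacterial or viral infection".

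The section also states its own standing. It opens with "Subjects should receive appropriate supportive care measures as deemed necessary by the treating investigator", and it says that the suggested measures "are outlined below and in greater detail in the ECI guidance document". On scope: "The treatment guidelines are intended to be applied when the investigator determines the events to be related to pembrolizumab". Section 5.2.1.2 (Dose Modification) sends investigators to both sources: "See Section 5.6.1 and Events of Clinical Interest Guidance Document for supportive care guidelines, including use of corticosteroids".

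**The concern.** A more severe event should not wait longer than a milder one for its first suggested anti-inflammatory treatment. Table 6 in Section 7.2.4 grades severity in the usual way: Grade 2 is moderate, Grade 3 is severe enough to indicate hospital care, and Grade 4 threatens life and calls for urgent action. The two bullets run against that order, and the documents give no reason for it. The same section asks sites to watch these patients for bowel perforation, so the protocol recognizes the danger.

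What is at stake is patient safety, not inference. An investigator who followed the bullets to the letter would start steroids later in the sicker patient.

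**Working it through.** The plan gives no calculated figure on this point, so there is none to reproduce. The check compares two thresholds from Section 5.6.1.

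**Inputs.** Grade 2 trigger: more than 3 days. Grade 3-4 trigger: more than 1 week, that is, more than 7 days. Convention assumed here: day 1 is onset, and a trigger of more than *k* days is first met on day *k* + 1.

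**Grade constant from onset.**

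| | Trigger | First day under a steroid instruction |
|---|---|---|
| Grade 2 | > 3 days | 3 + 1 = day 4 |
| Grade 3-4, as written | > 7 days | 7 + 1 = day 8 |
| Grade 3-4, if set at > 3 days | > 3 days | 3 + 1 = day 4 |
| Grade 3-4, if no wait | none | day 1 |

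- Gap as written: 8 - 4 = 4 days. On days 4 to 7 a Grade 2 patient is under a steroid instruction and a Grade 3-4 patient is not.
- Gap with a trigger of more than 3 days: 4 - 4 = 0.
- Gap with no wait: 1 - 4 = -3, so Grade 3-4 comes 3 days before Grade 2.

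**Worsening from Grade 2.** A patient at Grade 2 for more than 3 days before worsening is already under the oral steroid bullet and is not affected. A patient at Grade 2 for *d* = 1, 2 or 3 days who then worsens is affected. The text does not say whether the days at Grade 2 count toward the week.

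- If they count, the first instruction comes on day 8 from onset, and the gap against day 4 is 4 days.
- If the clock restarts at worsening, it comes on day *d* + 8, and the gap is *d* + 4 = 5, 6 or 7 days.

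**Is there an earlier trigger elsewhere?** None appears in the supplied text. Table 3 in Section 5.2.1.2 covers only pembrolizumab dosing: hold at Grade 2-3, stop permanently at Grade 4. Section 5.5.2 exempts steroids for suspected immune-related events from its prohibition but sets no timing.

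**Effect on the safety endpoint.** Section 4.2.3.2 counts related Grade 3 or higher immune-related toxicity as a DLT, and its exceptions do not include diarrhea/colitis. A related Grade 3-4 event counts whenever steroids start. The Section 8.2 limits (11 or more of 34 too toxic, 8 or fewer safe to proceed) do not depend on this bullet.

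**The case against.** The strongest reply is that the bullet does little harm in practice. The section is advisory and leaves supportive care to the investigator. Section 5.5.1 allows any treatment judged necessary, and Section 5.5.2 allows steroids for a suspected immune-related event. Perforation monitoring, fluids, consideration of GI consultation and endoscopy, and the hold or stop of pembrolizumab all apply without waiting a week. The ECI guidance document, which was not supplied, may give an earlier trigger. All of this stands. It makes the practical effect uncertain but does not correct the written order. If the ECI document does set an earlier trigger, the protocol conflicts with its own companion document.

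A second reply is that the regimens differ. Grade 2 gets oral steroids, while Grade 3-4 gets intravenous and then high-dose oral treatment, so the week might be a threshold for escalation. The text does not say so. The work-up bullet is written for Grade 2 and above, but the oral steroid bullet names Grade 2 alone, which leaves Grade 3-4 with no earlier oral instruction. The difference in regimen is a good reason to state the gap in days and not as a ratio of waits.

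A third reply is that infection must be excluded first. That requirement covers every disorder and applies equally at Grade 2, so it cannot explain a longer wait at Grade 3-4.

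A reader might infer that the protocol tells investigators to withhold steroids for a week. It does not; it only gives no earlier suggestion. A reader might also argue from the other events in the section, which carry no wait at Grade 3-4, that no wait must be right here. That comparison is weak, because diarrhea/colitis is also the only event in the section with a steroid wait at Grade 2.

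**Conclusion.** The concern holds as a defect in the written guidance: for diarrhea/colitis the suggested steroid trigger is inverted by grade. The size is 4 days (day 4 against day 8) at constant grade. It is 4 to 7 days for a patient who worsens within 3 days of Grade 2 onset, depending on whether time at Grade 2 counts. These figures assume a literal reading with day 1 as onset. They apply to pembrolizumab-related Grade 3-4 events that last long enough to reach the gap, in patients not already on steroids under the Grade 2 bullet.

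The documents do not show that patients would in fact be treated late, because discretion and the unseen ECI document may prevent it. The number affected is unknown, since no expected incidence of Grade 3-4 colitis is given. They also do not support an inference that the DLT endpoint or its operating characteristics are affected. The bullet should be corrected on patient-safety grounds.

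**What to change.** In the Grade 3-4 diarrhea/colitis bullet of Section 5.6.1, replace the one-week condition so that the trigger is no later than the Grade 2 trigger: at most more than 3 days, or no wait. State that time at Grade 2 counts toward it; otherwise a patient who worsens early could still wait longer than one who stays at Grade 2. The clinical lead should confirm the exact value and reconcile it with the ECI guidance document, whichever option is chosen. The supplied documents do not establish which value is clinically right. Keep the infection rule-out and the endoscopy step.

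The cost is one bullet of protocol text and one document check. The clinical downside is earlier steroid exposure in some patients, possibly before infection is fully ruled out. At constant grade this is up to 8 - 4 = 4 days earlier with a trigger of more than 3 days, or up to 8 - 1 = 7 days earlier with no wait.

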5.7 Diet/Activity/Other Considerations

5.7.1 Diet

Subjects should maintain a normal diet unless modifications are required to manage an AE such as diarrhea, nausea or vomiting.

5.7.2 Contraception

Pembrolizumab may have adverse effects on a fetus in utero. Furthermore, it is not known if pembrolizumab has transient adverse effects on the composition of sperm. Non-pregnant, non-breast-feeding women may be enrolled if they are willing to use 2 methods of birth control or are considered highly unlikely to conceive. Highly unlikely to conceive is defined as 1) surgically sterilized, or 2) postmenopausal (a woman who is ≥ 45 years of age and has not had menses for greater than 1 year will be considered postmenopausal), or 3) not heterosexually active for the duration of the study. The two birth control methods can be either two barrier methods or a barrier method plus a hormonal method to prevent pregnancy. Subjects should start using birth control from study Visit 1 throughout the study period up to 120 days after the last dose of study therapy.

The following are considered adequate barrier methods of contraception: diaphragm, condom (by the partner), copper intrauterine device, sponge, or spermicide. Appropriate hormonal contraceptives will include any registered and marketed contraceptive agent that contains an estrogen and/or a progestational agent (including oral, subcutaneous, intrauterine, or intramuscular agents).

Subjects should be informed that taking the study medication may involve unknown risks to the fetus (unborn baby) if pregnancy were to occur during the study. In order to participate in the study they must adhere to the contraception requirement (described above) for the duration of the study and during the follow-up period defined in section 7.2.2-Reporting of Pregnancy and Lactation to the Sponsor and to Merck. If there is any question that a subject will not reliably comply with the requirements for contraception, that subject should not be entered into the study.

5.7.3 Use in Pregnancy

If a subject inadvertently becomes pregnant while on treatment with pembrolizumab, the subject will immediately be removed from the study. The site will contact the subject at least monthly and document the subject's status until the pregnancy has been completed or terminated. The outcome of the pregnancy will be reported to the Sponsor and to Merck without delay and within 24 hours to the Sponsor and within 2 working days to Merck if the outcome is a serious adverse experience (e.g., death, abortion, congenital anomaly, or other disabling or life-threatening complication to the mother or newborn).

The study investigator will make every effort to obtain permission to follow the outcome of the pregnancy and report the condition of the fetus or newborn to the Sponsor. If a male subject impregnates his female partner the study personnel at the site must be informed immediately and the pregnancy reported to the Sponsor and to Merck and followed as described above and in Section 7.2.2.

